This is a phase II proof of concept (POC), multi-center, prospective, randomized, placebo-controlled, Sequential Parallel Comparison Design (SPCD) study, in which a total of 60 subjects with schizophrenia will be randomized studywide.

The study will be conducted in two phases. The study treatment will be administered in a double-blind fashion for all subjects throughout both phases of the study. A total of 60 subjects with schizophrenia will be randomized in a 1:1:1 ratio to one of three treatment sequences: drug-drug, placebo-drug, or placebo-placebo. Subjects will be randomized directly following confirmation of eligibility (at completion of Visit 2). Subjects randomized to the drug-drug sequence (n=20) will receive i.v. sodium nitroprusside (0.5 µg/kg/min for 4 hours) at Day 0 and Day 14. Subjects randomized to the placebo-drug sequence (n=20) will receive i.v. placebo at Day 0 and i.v. sodium nitroprusside (0.5 µg/kg/min for 4 hours) at Day 14. Subjects randomized to the placebo-placebo sequence (n=20) will receive i.v. placebo at Day 0 and again at Day 14. The double-blind treatment will be divided into two phases: Phase 1 from Day 0 to Day 14, and Phase 2 from Day 14 through Day 28.

At the end of Phase 1 the randomized subjects will be assessed and categorized into responders and non-responders, based on 20% or more reduction in their PANSS total score between Visit 4 (Baseline, Day 0) and Visit 7(Day 14). The data from the subjects deemed placebo non-responders in Phase 1 who go on to either stay on placebo or to receive treatment with sodium nitroprusside will be pooled with the data from Phase 1 from all subjects, according to SPCD.

Figure 1 –

Nitroprusside SPCD Study Design

Efficacy analysis is based on results of the 10 groups in green boxes

[figure not shown]
[figure not shown]

Figure 2 – Study Schemata

Study Visit Overview

Screening

- Visit 1 (Screening Visit, Day -28 to -14): Consists of signing a HIPAA compliant informed consent form and study qualification based on evaluation of inclusion/exclusion criteria. Medical records will be requested from the participant's primary care physician for confirmation of relevant eligibility criteria.
- Visit 2 (Remote Independent Interview, Day -13 to -3): Consists of independent assessment to confirm the diagnosis and the appropriateness of the subject for the study. Eligibility will also be assessed at this visit by conducting a PANSS,

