A 10-minute run-in period ("Phase I") has been added to ensure that the patient tolerates the drug. As determined by consulting cardiologist, this will include the administration of the drug at half of the rate (0.25 mcg/kg/min). The following Safety parameters will be followed for Phase I:

Safety Parameters

Safety Parameters Phase I dose:

- If SBP \leq 89 STOP infusion. Lie flat, feet up, call N.P. & P.I.
- If HR $>$ 120 bpm or $>$ 20 bpm over baseline HR, abort study
- If SpO2 $<$ 92%, stop infusion
- If patient reports headache, ask: "do you feel this headache is tolerable?"
 - If patient says "yes," continue dose
 - If patient says "no," STOP dose

-If patient experiences symptomatic hypotension (nausea, dizziness) STOP infusion.

If Phase I is tolerated per the above guidelines after the 10 minute run-in period, the drug will be administered at the rate of 0.5 mcg/kg/min ("Phase II") with the following parameters:

Safety Parameters for Phase II dose:

- If SBP between 81 and 89, lower dose to Phase I dose for 15 min. Monitor with CRC NP.
- If SBP rises to > 89mm Hg continue Phase I dose
- If SBP remains between 81 and 89mm Hg abort and call P.I.
- If SBP < 80, STOP infusion, lie flat, feet up & call P.I.
- If HR > 120 bpm or > 20 bpm over baseline HR, lower dose to Phase I dose for 15 min
- If SpO2 < 92% Stop infusion
- If patient reports headache, ask, "Do you feel this headache is tolerable?"
 - If patient says "yes", continue dose
 - If patient says "no", *lower dose to Phase I dose for 15 min*
- If better, continue Phase I dose
- If still intolerable, STOP dose
- If patient experiences symptomatic hypotension (nausea, dizziness) *lower dose to Phase I dose for 15 min*
- If better, continue Phase I dose
- *If not, Stop infusion, call P.I.*

Should the patient require PRN rescue medications, the following procedures will take place:

PRN Rescue medications:

In consultation with CRC N.P.

For SBP < 80 mmHg, may give 250 ml 0.9% NS

IV bolus via Sigma pump @999 ml/hr over 15 min X 2

For rash may give

Diphenhydramine 25 mg by mouth X 1

The IV line will be left in place for at least 1 hour following the infusion to allow for additional medications to control emergent side effects. If additional IV medication is necessary, an anesthesiologist, cardiologist, or medically qualified designate will start the infusion and a medical team will be present during the entire infusion period.

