### Treatment Groups

The following treatment groups will be assessed:

Table 4. Study Treatments

Group	Description
Test Treatment	Sodium Nitroprusside (0.5 µg/kg/min for 4 hours)
Control Treatment	Placebo (5% dextrose for 4 hours)

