## **Safety Population**

The Safety population is defined as any subject receiving the treatment after randomization. This population will be used for the analysis of safety parameters.

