## **Safety Analyses**

### Adverse Events

Adverse events will be coded using MedDRA. Treatment Emergent AE's (TEAE) are defined as events with an onset on or after the first randomized treatment. TEAEs will be summarized by treatment group and by stage of the study, System Organ Class, and preferred term. The following TEAE summaries will be provided:

- TEAEs by severity grade
- TEAEs by relationship to study treatment.

In addition, separate summaries of serious adverse events, and adverse events resulting in discontinuation of study treatment will be presented.

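### The Stage 2 adverse event table pools first and second nitroprusside infusions, and no planned table brings all first infusions together

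*SAP*

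**What the plan says.** I use Stage 1 for Day 0 to Day 14 and Stage 2 for Day 14 to Day 28.

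- **Groups.** SAP, Treatment Groups, opens with "The following treatment groups will be assessed" and lists two: nitroprusside and placebo. Protocol section M has the same table.
- **Tabulation.** SAP, Safety Analyses, Adverse Events: "TEAEs will be summarized by treatment group and by stage of the study, System Organ Class, and preferred term". Protocol section M repeats this. Neither document plans a safety table by sequence, infusion number or prior exposure.
- **Safety set.** SAP, Safety Population: "The Safety population is defined as any subject receiving the treatment after randomization". There is one set for the whole trial, and no denominator is stated for Stage 2 percentages.
- **Design.** Protocol section F has 60 subjects "randomized in a 1:1:1 ratio to one of three treatment sequences: drug-drug, placebo-drug, or placebo-placebo". It continues: "Subjects randomized to the drug-drug sequence (n=20) will receive i.v. sodium nitroprusside" on both infusion days, and "Subjects randomized to the placebo-drug sequence (n=20) will receive i.v. placebo at Day 0 and i.v. sodium nitroprusside" at Day 14.
- **Listings.** SAP, General Statistical Considerations, lists all collected data by subject.

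**The concern.** Safety and tolerability are the only stated secondary objective (Protocol section E). Two questions matter: how often a first nitroprusside infusion causes a reaction, and whether a second one behaves differently. A Stage 2 column that pools both kinds of infusion answers neither.

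The pooling also hides a good comparison. Placebo-drug and placebo-placebo subjects were assigned at the outset, and both received blinded placebo at Day 0. Losses before Day 14 therefore arise under identical treatment. Those who start the second infusion form a concurrent randomized comparison of a first nitroprusside infusion with placebo. Drug-drug subjects come to Day 14 by a different route, and adding them to the drug column blurs that contrast. The efficacy plan already keeps them apart: SAP, Analysis Populations, restricts the Stage 2 efficacy comparison to placebo non-responders. The safety plan makes no such distinction.

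**Working it through.** The documents give no adverse event rate and no safety precision target, so there is no safety figure to reproduce. The only computed figure is the 81% power. With Stage 1 at 20 against 40, Stage 2 at 20 × 0.7 × 0.8 = 11.2 per arm, and SD 14:

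- SE1² = 196 × (1/20 + 1/40) = 14.7 and SE2² = 196 × (2/11.2) = 35
- 10 / [0.5 × √(14.7 + 35)] = 2.837
- Φ(2.837 − 1.96) = 81.0%

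This agrees with the plan, and nothing below changes it.

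**Inputs from the documents:** 20 subjects per sequence (Protocol section F); 20% attrition by Week 4 (SAP, Sample Size Determination and Rationale). **Assumed for illustration:** first-infusion rate p1 = 20%; ratio r of second- to first-infusion rate from 0 to 1.5.

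**Step 1. What each column contains.**

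| Sequence | Stage 1 | Stage 2 |
|---|---|---|
| drug-drug (20) | first nitroprusside | second nitroprusside |
| placebo-drug (20) | placebo | first nitroprusside |
| placebo-placebo (20) | placebo | placebo |

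With two groups by stage, Stage 1 shows 20 on drug (all first infusions) against 40 on placebo. Stage 2 shows 40 on drug (20 first, 20 second) against 20 on placebo.

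**Step 2. The Stage 2 drug rate.** (20·p1 + 20·r·p1)/40 = p1(1+r)/2. Equal attrition in the two sequences, for example 16 and 16, leaves this unchanged.

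**Step 3. The denominator.** If all 20% attrition fell before Day 14, 32 of the 40 would be infused. If percentages were still taken over 40, the rate would be multiplied by 32/40 = 0.8. With attrition before Day 14 between 0 and 20%, the factor lies between 1.0 and 0.8.

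| r (p1 = 20%) | Denominator = infused | Denominator 40, 32 infused |
|---|---|---|
| 0 | 10% | 8% |
| 0.5 | 15% | 12% |
| 1 | 20% | 16% |
| 1.5 | 25% | 20% |

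**Step 4. What combining first infusions gains.** Stage 1 drug contributes 20 and Stage 2 placebo-drug contributes 16 to 20, so n = 36 to 40. With no event seen, the one-sided 95% upper bound is 1 − 0.05^(1/n):

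- n = 20: 13.9%
- n = 36: 8.0%
- n = 40: 7.2%

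This gain does not depend on r.

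**The case against.** A reader might infer that the plan understates the rate of first-infusion reactions. The documents do not support that.

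- **An unmixed estimate exists.** Every Stage 1 nitroprusside recipient is on a first infusion, and the tables are split by stage. The SAP never presents the Stage 2 rate as a first-infusion rate.
- **The direction is unknown.** Mixing dilutes only if r<1, and no passage gives r. One can argue that drug-drug subjects who reacted at Day 0 will be missing at Day 14, but this is not documented. The rule ending "20 bpm over baseline HR, abort study" (Protocol section H, Safety Parameters) belongs to the 10-minute half-rate run-in. At the full rate the same heart-rate trigger leads to a dose reduction. The section does not say that a stopped or reduced infusion bars the second one, and Protocol section I commits to every effort to keep subjects in for both periods.
- **The denominator is unstated.** The Safety Population section says who belongs to the set. It does not say that the whole set is the Stage 2 denominator, and a by-stage table may well count only those treated in that stage.

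It can also be said that safety reporting here is descriptive and that the subject listings allow any regrouping later. That is true, but a regrouping chosen after unblinding is weaker than a planned table. Finally, treatment group might have been meant as sequence in this context. The SAP does not say so, and its only definition has two groups.

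All of this stands against a claim of bias. None of it removes the pooling.

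**Conclusion.** Followed as written, the plan gives a Stage 2 nitroprusside rate built from about 20 first and about 20 second infusions. That rate cannot be read as either. Relative to p1 it is diluted if r<1, unbiased if r=1 and inflated if r>1; since r is not documented, the finding concerns interpretability and not the direction of an error. The 20% rate in the table above is illustrative only.

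The firmer loss is precision. First-infusion safety rests on about 20 subjects in the Stage 1 column, although 36 to 40 will have had a first infusion. That range rests on 20 per sequence and on no more than the planned 20% attrition falling before Day 14. This is an inexpensive improvement to a stated tabulation. It does not affect the efficacy analysis, sample size or power.

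**What to change.** In SAP, Safety Analyses, Adverse Events, and the matching part of Protocol section M:

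1. Show Stage 2 TEAEs by sequence: drug-drug, placebo-drug, placebo-placebo.
2. State that the denominator in each stage is the subjects who started that stage's infusion.
3. Add one first-infusion table that combines Stage 1 nitroprusside with Stage 2 placebo-drug. Show each part against the placebo subjects of the same stage before giving the combined figure, since the Stage 2 subjects have already had one placebo infusion.
4. Treat TEAE-related discontinuations and withdrawals in the same way.

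The cost is a few extra columns and one table, with no new data. Cells will be small, at 16 to 20 per sequence. Some subjects appear in both parts of the first-infusion table (placebo-drug subjects as Stage 1 placebo and then as Stage 2 drug), so the table should stay descriptive.

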#### Abnormal Involuntary Movement Scale (AIMS)

All the data from the AIMS will be listed and the percent change in the total score will also be presented.

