It is up to the study physician to determine if symptoms represent either a worsening of pre-existing conditions or an unfavorable/ unintended sign, symptom or disease which is temporally related with study participation; and to document AEs in the AE log accordingly.

Abnormal Involuntary Movement Scale (AIMS) (Riezen 1988)

The AIMS is a 12-item scoring tool that is commonly used to monitor the occurrence and severity of tardive dyskinesia for patients receiving neuroleptic medications. In this study,

the highest severity observed for each item on the AIMS scoring sheet will be recorded. For movements that occur upon activation, one severity grade less than the spontaneously observed movement will be selected for the item. The 12-item AIMS to be used in this study consists of five categories, as outlined below:

- I. **Facial and Oral Movements** (items 1 through 4) includes an item for each of the following: muscles of facial expression, lips and perioral area, jaw, and tongue. Each item will be assessed using a 5-point scale (0 = none, 1 = minimal (may be extreme normal), 2 = mild, 3 = moderate, and 4 = severe).
- II. **Extremity Movements** (items 5 and 6) includes an item for each of the following: upper extremities (including arms, wrists, hands, and fingers) and lower extremities (including legs, knees, ankles, and toes). Each of these items will be assessed using the same 5-point scale as items 1 through 4.
- III. **Trunk Movements** (item 7) includes one item for assessing the movements in the neck, shoulders, and hips. This item will be assessed using the same 5-point scale as items 1 through 4.
- IV. **Global Judgment** (items 8 through 10) includes three items. Item 8 assesses severity of abnormal movements overall. Item 9 assesses the severity of incapacitation due to the abnormal movements. These two items (i.e., items 8 and 9) will be assessed using the same 5-point scale as items 1 through 4. Item 10 assesses the subject's awareness of his/her abnormal movements, as judged by the subject. For Item 10, the following 5-point scale will be used: 0 = no awareness; 1 = aware, no distress; 2 = aware, mild distress; 3 = aware, moderate distress; 4 = aware, severe distress.

The Columbia Suicide Severity Rating Scale (C-SSRS) (Posner 2007):

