#### Safety Assessments

- Incidence of Treatment-Emergent Adverse Events (TEAE)

- Incidence of withdrawals from the study due to TEAEs
- Percent change in Abnormal Involuntary Movement Scale (AIMS)
- Percent change in Systematic Assessment for Treatment Emergent Effects–Systematic Inquiry (SAFTEE-SI)
- Assessment of suicidality per the Columbia-Suicide Severity Rating Scale (C-SSRS)
- Changes in blood pressure and heart rate
- Changes in electrocardiogram (ECG) parameters

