## **Sample Size Determination and Rationale**

Sixty (60) subjects will be randomized in an effort to assure that 48 subjects complete the study.

The RCT Logic Calculator (by Schoenfeld, D and Ivanova,A; <http://www.rctlogic.com/calculator/calculator-continuous.aspx>) was used for this sample size calculation. This sample size will provide “sufficient” statistical power for the selected primary endpoint. The sample size calculation is based on the assumption that there is a clinically meaningful weighted (50%) average difference of 10 points (9 points in Stage 1 and 11 points in Stage 2) between sodium nitroprusside and placebo group accordingly, (with standard deviation of 14) in PANSS total scores after 2 weeks of treatment between the two treatment groups. This power calculation is based on a 20% attrition by Week 4 and 30% placebo response at the end of Stage 1. Under the above assumptions, 60 subjects will be required to meet the Type I error rate of 0.05 and an 81% power.

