## **General Statistical Considerations**

All collected study data will be presented in subject data listings. Statistical analyses will be performed using SAS® for Windows, version 9.3 or later. Descriptive statistics (n, mean, standard deviation, median, minimum and maximum) will be calculated by treatment group for continuous variables. Frequencies and percentages will be presented by treatment group for categorical variables.

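### AIMS change is planned only as percent change in the total; taken per subject it has no value at a baseline of 0, so this safety summary can miss new-onset movement

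*SAP*

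**What the plan says.** The safety list in the SAP (Safety Assessments) names the measure as "Percent change in Abnormal Involuntary Movement Scale (AIMS"). The AIMS paragraph under SAP Safety Analyses adds: "All the data from the AIMS will be listed and the percent change in the total score will also be presented". Section M of the protocol has the same two statements. No absolute change, shift table or count of subjects who worsened is named for AIMS.

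Protocol Section H, Safety Measures, describes the scale as "commonly used to monitor the occurrence and severity of tardive dyskinesia". For items 1 to 4 it says "Each item will be assessed using a 5-point scale (0 = none"; items 5 to 9 use the same scale, and item 10 also starts at 0. On content it says "The 12-item AIMS to be used in this study consists of five categories", but the text then describes four categories and 10 items. Appendix 5 gives only a link to a form.

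The Synopsis includes AIMS among the measures for the secondary (safety and tolerability) outcomes and schedules it at Visits 3, 4, 6, 7 and 9. For continuous data in general, the SAP says: "Descriptive statistics (n, mean, standard deviation, median, minimum and maximum) will be calculated by treatment group for continuous variables". The SAP paragraph on missing data covers efficacy data only.

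**The concern.** Percent change divides by the baseline score. A subject with a baseline AIMS total of 0 therefore has no percent change, whatever happens afterwards. Nothing in the eligibility criteria rules out a total of 0, and nothing in the plan says what to do with one.

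The loss is one-sided. A subject at 0 can only stay there or worsen, so leaving such subjects out removes possible worsening and no possible improvement. A move from 0 to a positive score is the occurrence of abnormal movement, which the protocol itself gives as one of the two things the scale monitors. Just above 0 the measure exists but is unstable, because a one-point difference gives very different percentages depending on where the subject began.

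At stake is whether the AIMS table can show new-onset movement by treatment group. No test, threshold or decision rule is tied to AIMS.

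**Working it through.** **The plan's own figure.** The documents give no number for AIMS. The only related figure is the 81% power for the PANSS endpoint, checked here to confirm the sample-size inputs. Inputs (SAP, Sample Size Determination and Rationale): differences of 9 and 11 points, weight 0.5, SD 14, 20% attrition, 30% placebo response. Stage 1 is 20 v 40; Stage 2 is 20 × 0.8 × 0.7 = 11.2 per arm.

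- SE = √[0.25 × 14² × (1/20 + 1/40) + 0.25 × 14² × (2/11.2)] = 3.525
- Power = Φ(10/3.525 − 1.96) = 81.0%

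The stated power is reproduced, and nothing below alters it.

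**Per subject or group mean?** The AIMS paragraph does not say. The general rule that continuous variables get an SD, median and range needs one value per subject, so the per-subject reading is the natural one.

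**Behaviour of the measure.** Percent change = 100 × (follow-up − baseline)/baseline.

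- Baseline 0: changes of 0 to 2, 0 to 6 and 0 to 12 are all undefined; the absolute changes are 2, 6 and 12.
- A one-point rise is 100/1 = +100% from 1, 100/2 = +50% from 2, and 100/4 = +25% from 4.

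**Subjects without a value.** The share at baseline 0 is not in the documents; 20%, 50% and 80% are assumptions. The Safety population is the base ("The Safety population is defined as any subject receiving the treatment after randomization").

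Stage 1 takes all 60 randomized as treated and assessed, which is an upper bound: 20 on nitroprusside and 40 on placebo. Stage 2 uses the plan's attrition ("This power calculation is based on a 20% attrition by Week 4"): 60 × 0.8 = 48, assumed to be 16 per sequence. That gives 16 + 16 = 32 on nitroprusside and 16 on placebo, with the same share assumed to be at 0 at Visit 6.

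| Assumed share at 0 | Stage 1 missing of 60 | Left: drug (of 20) / placebo (of 40) | Stage 2 expected missing of 48 | Left: drug (of 32) / placebo (of 16) |
|---|---|---|---|---|
| 20% | 12 | 16 / 32 | 9.6 | 25.6 / 12.8 |
| 50% | 30 | 10 / 20 | 24 | 16 / 8 |
| 80% | 48 | 4 / 8 | 38.4 | 6.4 / 3.2 |

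**One-sidedness (constructed example).** Take 60 subjects, a 10% chance of a rise at every baseline, and a 10% chance of a fall for those above 0. Expected rises are 60 × 0.10 = 6. Percent change keeps 6 × (0.8, 0.5, 0.2) = 4.8, 3.0 or 1.2 of them. Expected falls are 60 × (0.8, 0.5, 0.2) × 0.10 = 4.8, 3.0 or 1.2, and all are kept.

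**Small illustration (assumed data).** Of 20 subjects, 12 start at 0 and 4 of these rise to 6; the other 8 stay at 4. Per-subject percent change uses 8 subjects and averages 0%. Absolute change uses all 20 and averages 24/20 = +1.2 points, with 4 new-onset cases visible. Percent change of the group totals would be 100 × (56 − 32)/32 = 75%.

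**The total.** With items 1 to 7 the maximum is 7 × 4 = 28; with items 1 to 10 it is 10 × 4 = 40. The documents do not say which items, or whether any beyond the 10 described, are included.

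**The case against.** The strongest counter-argument is that new-onset movement has other routes into the report. All AIMS scores are listed. The SAP promises generic descriptive summaries of all collected data, and a rise from 0 would move those. The protocol (Clinical Laboratory Adverse Events) makes changes in study assessments reportable as adverse events when judged clinically significant, so such a rise would reach the adverse event tables by treatment and stage. This stands, and it limits the consequence to one descriptive table. It does not repair the table. Listings do not compare groups, the generic summaries name no AIMS change and no count of subjects who worsened, and the adverse event route depends on the investigator's judgement of clinical significance.

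A group-mean percent change would stay defined unless the group mean were 0. That is true, but the plan does not choose that reading.

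Stage 1 losses depend on a score taken before any infusion, so the same share is expected to drop out of each arm. This also stands: for Stage 1 the problem is lost coverage, not demonstrated bias between arms. It does not carry over to Stage 2 if Visit 6 is the baseline, because Visit 6 follows the first infusion.

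The magnitudes rest on assumed shares. The Stage 2 base of 48 also leaves out subjects assessed at Visit 7 who withdraw before Day 28. Both limits are accepted.

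Finally, the Schedule of Events marks two AIMS entries as discontinued from 10/2015. Its columns are broken in the available text, but the entries fit Visits 5 and 8, where the visit-by-visit lists include no AIMS. Those lists confirm AIMS at Visits 3, 4, 6, 7 and 9.

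**Conclusion.** The concern holds. Percent change in the total is the only AIMS change measure named, a baseline of 0 is possible, and no rule deals with it. On the per-subject reading, the summary leaves out the subjects in whom movement could newly appear. At assumed zero shares of 20% to 80%, that is 12 to 48 of 60 subjects in Stage 1 and an expected 9.6 to 38.4 of 48 in Stage 2. The true share cannot be known from the documents.

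The importance is low. The risks the protocol stresses are hypotension and cyanide toxicity; the primary endpoint, Type I error and 81% power are unaffected; and listings and adverse event tables remain. The SAP's general mention of analysis of covariance for continuous data is not taken here to cover AIMS. If it did, an analysis of percent change would lose the same subjects. This is an optional improvement, worth making because it is cheap.

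**What to change.** In protocol Section M and in the SAP (the Safety Assessments list and the AIMS paragraph in each), replace percent change with the following:

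- Absolute change in the AIMS total by treatment group and stage: from Visit 3 for Stage 1 and from Visit 6 for Stage 2.
- For Stage 2, also change from Visit 3 by treatment sequence, so that a movement that began in Stage 1 and persisted stays visible. A total of 0 at Visit 3, 3 at Visit 6 and 3 at Visit 9 is 3 − 3 = 0 from Visit 6 but 3 − 0 = +3 from Visit 3.
- The number of subjects with any increase, with 0 to above 0 shown separately.
- A statement of which items form the total.

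The absolute change and the counts are the core; the by-sequence display is a useful addition. Apply the same change to SAFTEE-SI only if its total can be 0, which the documents do not say.

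The cost is minor wording in both documents and minor programming. No new data are needed, since AIMS is already collected at Visits 3, 4, 6, 7 and 9. One drawback is that a count of any increase also picks up one-point rating noise, so it should be read beside the absolute change.
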